5.8.1 Adverse Events

Adverse events (AEs) will be collected from the time of informed consent throughout the study, up through the poststudy visit.

All AEs will be coded and classified according to MedDRA (Version 26.1 or later). The intensity of adverse events is judged by the Investigator as mild, moderate or severe; a causal relationship to study drug is judged by the Investigator as probably related, possibly related or unrelated; outcome of an adverse event is judged by the Investigator as recovered/resolved and not recovered/not resolved. Treatment-emergent adverse events (TEAEs) are defined as 1) AEs with an onset date and time after the first dose of study drug, or 2) any event already present that worsens in severity after exposure to the treatment.

A serious adverse event (SAE) is an AE occurring during any study phase (ie, baseline, treatment, or follow-up), and at any dose of the investigational product that fulfils one or more of the following: 1) Results in death; 2) It is immediately life-threatening; 3) It requires in-participant hospitalization or prolongation of existing hospitalization; 4) It results in persistent or significant disability or incapacity or substantial disruption of the ability to conduct normal life functions; 5) Results in a congenital abnormality or birth defect; 6) It is an important medical event that may jeopardize the participant or may require medical intervention to prevent one of the outcomes listed above. The following are considered events of clinical interest (ECIs):

- Overdose

- Alanine Aminotransferase (ALT) or Aspartate Aminotransferase (AST) $> 3 \times$ ULN, confirmed by repeat laboratory test
- Hypersensitivity Reactions

Significant adverse events of particular clinical importance, other than SAEs and those AEs leading to discontinuation of the participant from the study, will be classified as other adverse events (OAEs). For each OAE, a narrative may be written and included in the Clinical Study Report.

A summary table of AEs will be created containing: number of AEs, number of TEAEs, number of participants with TEAEs, number of participants with treatment-related TEAEs, number of serious TEAEs, number of participants with serious TEAE, number of participants with treatment-related serious TEAEs, number of serious AEs, number of participants with serious AEs, number of events of clinical interest (ECIs) and AEs leading to death, AEs leading to study discontinuation, AEs leading to treatment interruption, AEs leading to treatment discontinuation.

All TEAEs will be summarized as the number and percentage of participants by SOC, PT. Missing or partially missing start and end dates for AEs will be handled according to the conventions detailed in [Appendix A](#). For cases where ascertaining treatment-emergence is unlikely, the event will be categorized as treatment-emergent AE. Separate summaries will be created by severity and by relationship to study drug. If the same AE (PT) is reported more than once for the same participant, it will only be counted once in the summary table. For summary tables by severity and relationship to study drug, if the same AE (PT) is reported more than once for the same participant, the highest severity grade (severe $>$ moderate $>$ mild) or the strongest relationship to treatment (probably related $>$ possibly related $>$ unrelated) will be counted in the summary table. All SAEs, AEs leading to study discontinuation and AEs leading to death will be summarized by SOC and PT.

All AEs will be listed, and a flag will indicate if the AE is treatment emergent and a flag will indicate if the AE is unexpected adverse event.

All serious AEs (SAEs) will be listed, and a flag will indicate if the SAE is treatment emergent.

All adverse events leading to study discontinuation will be listed by participant.

All adverse events leading to death will be listed by participant. All ECI will be listed by participant.

5.8.2 Clinical Laboratory Assessments

Hematology, coagulation, blood chemistry, urinalysis, alcohol, and urine drug screens, pregnancy screen, serology, and COVID-19 test will be performed as described in the schedule of assessment [Table 1](#).

Descriptive statistics for baseline value, actual value will be provided for clinical hematology, coagulation, chemistry laboratory tests and quantitative urinalysis including pH. The change from baseline value to Day 5 post study will be provided for hematology

and clinical chemistry. Baseline for clinical laboratory tests is defined as the last non-missing assessment prior to administration of study drug. Conventional Units will be used for reporting the laboratory test results. Unscheduled lab visit assessments will be excluded from summary tables but will be provided in the listings.

Values for any chemistry, hematology, coagulation and urinalysis values outside the clinical reference ranges, clinically significant or not will be flagged on the individual participant data listings. Laboratory test results will be assigned a low/normal/high (L/N/H) classification according to whether the value is below (low, L), within (normal, N), or above (high, H) the laboratory parameter's reference range. Shifts from baseline (L/N/H) to Day 5 post study (L/N/H) will be presented for hematology and clinical chemistry only.

Plots will be generated for laboratory parameters, including the absolute values and change from baseline values for hematology and clinical chemistry.

Alcohol and urine drug screens, serology, COVID-19 test, pregnancy screen results will be listed by participant.

5.8.3 Vital Signs Assessments

Vital signs, including blood pressure (BP systolic and diastolic), heart rate, respiratory rate, and body temperature will be measured at the timepoints indicated in [Table 1](#).

All vital sign data including unscheduled records will be listed. Unscheduled records will be excluded from the summary statistics. Vital sign data including baseline value, actual value, and change from baseline to each post-baseline visit will be summarized by visit and timepoint. Abnormal or clinically significant (CS) vital signs will be flagged in the listings.

5.8.4 Physical Examinations

A standard physical examination will be performed at the timepoints indicated in [Table 1](#).

Physical examination results will be listed by participant in the safety population.

5.8.5 Electrocardiogram (ECG)

A safety 12-lead ECG will be obtained and evaluated by a physician for the presence of abnormalities at screening indicated in the Schedule of Assessments in [Table 1](#).

Participants should be resting in a semi-recumbent position for at least 10 minutes prior to having ECG readings obtained. ECG measurements will be single measurements.

Electrocardiogram examination will be listed for each ECG parameter in the safety population, including datetime collection, testing result, abnormal or not, clinically significant or not, specification if clinically significant.

5.9 Interim Analysis

An interim analysis will be conducted after five subjects have completed their

participation in the study. The analysis will involve the examination of pharmacokinetic and safety data and will comprise a full analysis as described in the SAP. The objective of the interim analysis is to determine whether the data from 5 participants is sufficient to address the objectives of the study and fulfill the post marketing requirement (PMR 4069-2); if not the study shall continue to recruit up to 10 participants.

The reporting analysis will involve descriptive statistical methods, including summaries, tabulations, graphs, or by-subject listings. Before initiating this analysis, the data for the study endpoints will undergo a thorough cleaning process, and the database will be soft-locked.

5.10 Statistical Programming and Deliverables

All statistical analyses, tables and listings will be generated in SAS (version 9.3 or later) with appropriate documentation and programming validation. The table of contents of all tables, figures, and listings will be presented in a TFLs shell supplemental document.

5.11 Changes to the Planned Analysis

Any deviation(s) of consequence from the SAP during the data analysis will be documented and justified in an amended SAP and/or in the final report or addressed in a separate document, as appropriate.

APPENDIX A. ADVERSE EVENTS DATE IMPUTATION

AE Start Date	AE Stop Date	Algorithms
Known	Known	NA
	Partial	Impute stop date as the latest date possible (i.e., last day of month if day is missing or Dec 31 if day and month are missing). If the imputed stop date is later than the earlier date of data cutoff date and date of end of study, then use cutoff date or date of end of study, whichever is earlier, as the imputed AE stop date.
	Missing	Impute stop date as follows: (1) if study is ongoing: data cutoff date (2) if study discontinued: date of end of study
Partial	Known	Impute start date as follows: 1. If day missing only: (1) if same year-month as that of the start date of study drug: first dose date of study drug or AE end date, whichever is earlier (2) if different year-month from that of the start date of study drug: first day of month 2. If both month and day are missing: (1) if same year as that of the start date of study drug: first dose date of study drug or AE end date, whichever is earlier (2) if different year from that of the start date of study drug: January 1st of the year
	Partial	Impute start date as follows: 1. If day missing only: (1) if same year-month as that of the start date of study drug: first dose date of study drug (2) if different year-month from that of the start date of study drug: first day of month 2. If both month and day are missing: (1) if same year as that of the start date of study drug: first dose date of study drug (2) if different year from that of the start date of study drug: January 1st of the year
		Impute stop date as the latest date possible (i.e., last day of month if day is missing or Dec 31 if day and month are missing). If the imputed stop date is later than the earlier date of data cutoff date and date of end of study, then use cutoff date or date of end of study, whichever is earlier, as the imputed AE stop date.
	Missing	Impute start date as follows: 1. If day missing only: (1) if same year-month as that of the start date of study drug: first dose date of study drug (2) if different year-month from that of the start date of study drug: first day of month

		
2. If both month and day are missing:
 
(1) if same year as that of the start date of study drug: first dose date of study drug
 
(2) if different year from that of the start date of study drug: January 1st of the year
 
Impute stop date as follows:
 
(1) if study is ongoing: data cutoff date
 
(2) if study discontinued: date of end of study

Missing	Known	Impute start date as the first dose date of the study drug or AE end date, whichever is earlier.
	Partial	Impute start date as the first dose date of the study drug. Impute stop date as the latest date possible (i.e., last day of month if day is missing or Dec 31 if day and month are missing). If the imputed stop date is later than the earlier date of data cutoff date and date of end of study, then use cutoff date or date of end of study, whichever is earlier, as the imputed AE stop date.
	Missing	Impute start date as the first dose date of the study drug. Impute stop date as follows: (1) if study is ongoing: data cutoff date (2) if study discontinued: date of end of study

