### 11.7.1. Prestudy Screening (Day -28 to Day -1)

Screening and Day -1 procedures can be completed together the same day depending on when the participant is screened and able to be treated. Prestudy screening will occur within approximately 4 weeks prior to administration of the initial dose of study medication. Potential participants will be evaluated to determine that they fulfill the entry requirements as set forth in the inclusion and exclusion criteria. The investigator will discuss with each participant the nature of the study, its requirements, and its restrictions.

Prestudy screening will include the following procedures:

- Provision of written informed consent
- Adverse event surveillance from the time informed consent is obtained
- Review of inclusion/exclusion criteria
- Demographics information
- Medical history for the prior 1 year (including pregnancy, postpartum, and lactation history)
- Prior Medication review
- Physical examination, including body weight and height

- Vital signs (HR/BP/RR/Temp)
- 12-lead ECG
- Laboratory safety tests
- HIV/Hepatitis Screen
- Pregnancy test (serum)
- COVID, Alcohol and urine drug screen (site standard)

For details on the procedures, please refer to the Schedule of Assessments ([Table 5](#)).

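### Two places in SAP Appendix A omit the check of an imputed AE start against a partial stop date, so an event that ended before dosing can be given a start after its stop and may be counted as treatment-emergent

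*SAP*

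**What the plan says.** SAP Section 5.8.1 sends missing and partial AE dates to Appendix A. Three parts of that table matter.

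- **Start missing, stop partial.** "Impute start date as the first dose date of the study drug. Impute stop date as the latest date possible", the latest date being "last day of month if day is missing or Dec 31 if day and month are missing". The stop has one limit, an upper one that applies "If the imputed stop date is later than the earlier date of data cutoff date and date of end of study".
- **Start partial, stop partial, with start month and day both missing.** "if same year as that of the start date of study drug: first dose date of study drug". The stop is handled as above.
- **Start missing, stop known.** "Impute start date as the first dose date of the study drug or AE end date, whichever is earlier". The Partial/Known row applies the same limit in its dosing-month and dosing-year branches.

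Section 5.8.1 defines treatment-emergent events first as "AEs with an onset date and time after the first dose of study drug". It then adds a default: "For cases where ascertaining treatment-emergence is unlikely, the event will be categorized as treatment-emergent AE".

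The pre-dose period is covered by AE collection. Protocol Section 11.7.1 lists "Adverse event surveillance from the time informed consent is obtained", and screening may take place up to about 4 weeks before the first dose.

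**The concern.** A stop recorded only as a month and year can still settle the order of events. If the whole of that month precedes the first dose, the event ended before treatment. The rows with a known stop respect this by never letting the imputed start pass the stop. The two places with a partial stop do not, so the handling of the same event depends only on whether someone wrote down a day.

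Safety and tolerability form a secondary objective, and Section 5.8.1 summarises treatment-emergent events as numbers and percentages of participants. With an interim at 5 participants and a maximum of 10, one wrongly attributed event is visible in the tables.

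**Working it through.** The documents state no figure on this point. The check applies the Appendix A rules to assumed dates.

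**Inputs.** First dose 10 May 2024 (assumed). End of study is Day 5, so 14 May 2024. The data cutoff is taken to be no earlier than that.

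**Is the case reachable?** Counting back 28 days from 10 May gives 12 April. An AE collected after consent could therefore have stopped on any of the 19 days from 12 to 30 April and be recorded only as Apr 2024.

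**Rules as written.**
- Partial stop: derived stop = min(last day of recorded month, or 31 December if only the year is known; end of study).
- Missing start with partial stop, or year-only start in the dosing year with partial stop: derived start = first dose date.
- Missing start with known stop: derived start = min(first dose date, stop date).

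| Recorded start | Recorded stop | Derived start | Derived stop | Order |
|---|---|---|---|---|
| missing | Apr 2024 | 10 May 2024 | 30 Apr 2024 | start 10 days after stop |
| 2024 | Apr 2024 | 10 May 2024 | 30 Apr 2024 | start 10 days after stop |
| Apr 2024 | Apr 2024 | 1 Apr 2024 | 30 Apr 2024 | consistent, pre-dose |
| missing | 20 Apr 2024 | 20 Apr 2024 | 20 Apr 2024 | consistent, pre-dose |
| missing | May 2024 | 10 May 2024 | 14 May 2024 | consistent, order to dose undetermined |

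The first two rows are faulty. The upper limit does not help, because 30 April is already before 14 May.

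A year-only stop can cause the same fault when the start is missing. With an assumed dose on 10 January 2024 and a stop recorded as 2023, the start is 10 January 2024 and the stop 31 December 2023. This cannot happen in the Partial/Partial branch, where the start year is the dosing year and the stop cannot be in an earlier year. Nor does the fault arise when only the start day is missing. A start in the dosing month cannot have a stop in an earlier month, and a start in any other month is set to the first of that month.

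**Treatment-emergent flag.** The derived onset equals the dosing date and has no time, so it does not strictly meet the definition, which needs a date and time after dosing. The flag then depends on the default for unclear cases. Section 5.8.1 and Appendix A contain no instruction to look at the stop date. Appendix B does for the parallel medication case: with a missing start and partial stop, it imputes the stop and classes the medication as prior if that stop precedes study drug. A medication stopped in Apr 2024 would be prior, while the AE that it treated would start on the dosing date.

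**Size.** One participant is 1/5 = 20 percentage points at the interim, or 1/10 = 10 points at full size, assuming 5 or 10 in the safety population. Participants are counted once, so the change in overall incidence is 0 if she already has a treatment-emergent event.

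**With the limit applied.** Start = min(10 May, 30 April) = 30 April in both faulty rows: consistent and pre-dose. The May 2024 row does not change and still falls to the default.

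**The case against.** The strongest reply concerns the flag. Section 5.8.1 reserves its default for events whose status is hard to establish. If the recorded month shows that the event ended before dosing, the status is established, and a careful programmer would not flag it. That is a fair reading. A reader might infer that the SAP definitely counts such events as treatment-emergent, but the text does not go so far. It leaves the result to the programmer, with a derived start on the dosing date pointing the wrong way.

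The trigger is also narrow. Protocol Section 14.2.8 requires onset and resolution dates and times for every AE, surveillance is repeated predose, screening may be on the same day as Day -1, and data are cleaned before the interim. Someone would have to know roughly when an event stopped but not the month in which it began, within about 4 weeks and in at most about 10 women. This stands, and it limits the importance of the point. It does not remove the inconsistency, because Appendix A exists for the dates that cleaning cannot resolve.

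Two other inferences should be avoided. Inverted dates need not appear in the AE listing, since the SAP does not say whether listings show recorded or imputed dates. Only the derived dates are certain to be inverted. And the share of dosing dates for which consent falls in an earlier calendar month is not the probability of the problem, which depends on when AEs stop and on how often dates are incomplete.

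**Conclusion.** The gap is real but minor. In two places Appendix A drops a limit that it uses elsewhere. When the start has no month and the partial stop lies wholly before the first dose, the derived start follows the derived stop. That follows directly from the text; the example dates are assumed. Counting the event as treatment-emergent is possible under the Section 5.8.1 default but not certain. Not every partial stop is affected: an event with a known start, or with a start month recorded, is handled consistently.

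The 20 and 10 percentage points are ceilings for one false count, not expected effects. No expected number of cases can be given.

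**What to change.** In the Missing/Partial row, and in the Partial/Partial branch where start month and day are both missing and the start year is the dosing year, impute the stop first. Then set the start to the earlier of the first dose date and the imputed stop date, as the known-stop rows already do.

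Add to Section 5.8.1 that an AE whose recorded stop precedes the first dose, even if only month and year or year alone is known, is not treatment-emergent. State also that the default applies only when the recorded date parts leave the order undetermined.

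The cost is two table cells, a short addition to Section 5.8.1 and a small programming change. It needs no new data and no protocol amendment. Undetermined cases remain treatment-emergent, so the conservative intent of the default is kept.

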APPENDIX B. CONCOMITANT MEDICATIONS DATE IMPUTATION

CM Start Date	CM Stop Date	Algorithms
Known	Known	
If stop date < start date of study drug: PRIOR
 
If stop date \geq start date of study drug, and start date \leq end of study: CONCOMITANT
 
If stop date \geq start date of study drug and start date $>$ end of study: POSTTREATMENT

	Partial	
Impute stop date as the latest date possible (i.e., last day of month if day missing or Dec 31 if day and month are missing), then:
 
If stop date < start date of study drug: PRIOR
 
If stop date \geq start date of study drug, and start date \leq end of study: CONCOMITANT
 
If stop date \geq start date of study drug, and start date $>$ end of study: POSTTREATMENT

	Missing	
No PRIOR assignment if stop date is missing
 
If start date \leq end of study: CONCOMITANT
 
If start date $>$ end of study: POSTTREATMENT

Partial	Known	
Impute start date as the earliest date possible (i.e., first day of month if day missing or Jan 01 if day and month are missing), then:
 
If stop date < start date of study drug: PRIOR
 
If stop date \geq start date of study drug and start date \leq end of study: CONCOMITANT
 
If stop date \geq start date of study drug and start date $>$ end of study: POSTTREATMENT

	Partial	
Impute start date as the earliest date possible (i.e., first day of month if day missing or Jan 01 if day and month are missing) and impute stop date as the latest date possible (i.e., last day of month if day is missing or Dec 31 if day and month are missing), then:
 
If stop date < start date of study drug: PRIOR
 
If stop date \geq start date of study drug and start date \leq end of study: CONCOMITANT
 
If stop date \geq start date of study drug and start date $>$ end of study: POSTTREATMENT

	Missing	
No PRIOR assignment if stop date is missing
 
Impute start date as the earliest date possible (i.e., first day of month if day is missing or Jan 01 if day and month are missing), then:
 
If start date \leq end of study: CONCOMITANT
 
If start date $>$ end of study: POSTTREATMENT

CM Start Date	CM Stop Date	Algorithms

Missing	Known	No POSTTREATMENT assignment if start date is missing If stop date < start date of study drug: PRIOR If stop date \geq start date of study drug: CONCOMITANT
	Partial	No POSTTREATMENT assignment if start date is missing Impute stop date as the latest date possible (i.e., last day of month if day missing or Dec 31 if day and month are missing), then: If stop date < start date of study drug: PRIOR If stop date \geq start date of study drug: COMCOMITANT
	Missing	CONCOMITANT
